#### **Complete Remission (CR) at 12 and 18 months**

In the Rituxan group, 44% of patients achieved CR at 6 and 12 months, and 38% of patients achieved CR at 6, 12, and 18 months. In patients treated with cyclophosphamide (followed by azathioprine for maintenance of CR), 38% of patients achieved CR at 6 and 12 months, and 31% of patients achieved CR at 6, 12, and 18 months.

#### **Retreatment with Rituxan**

Based upon investigator judgment, 15 patients received a second course of Rituxan therapy for treatment of relapse of disease activity which occurred between 8 and 17 months after the first course of Rituxan. The limited data preclude any conclusions regarding the efficacy of subsequent

**For information on azathioprine, please see:**[http://www.accessdata.fda.gov/drugsatfda\\_docs/label/2011/016324s034s035lbl.pdf](http://www.accessdata.fda.gov/drugsatfda_docs/label/2011/016324s034s035lbl.pdf)**For information on Mycophenolate Mofetil, please see:**[http://www.gene.com/download/pdf/cellcept\\_prescribing.pdf](http://www.gene.com/download/pdf/cellcept_prescribing.pdf)**1.4 Dose Rationale and Risk/Benefits**

B cells are commonly identified by the presence of either CD20 or CD19. Developmentally, CD19 is expressed earlier than CD20 and continues to be expressed after CD20 expression is lost during B cell differentiation to plasma cells. To maximize detection of B cells, we will employ CD19 in flow cytometric analysis of CD5+ B cells.

Patients whose CD5+ B cells account for 43% or greater of total CD19 B cells will be randomized to either NO maintenance therapy or to maintenance therapy with rituximab 500 mg IV every 6 months starting when the CD19+ B cells are  $\geq 1\%$  of total lymphocytes (and CD5+ B cells are measurable) and at least 4 weeks after the last dose of cyclophosphamide (for patients who received cyclophosphamide induction therapy). Patients who are allergic or intolerant to rituximab or cannot access rituximab (e.g. insurance reasons) will receive maintenance therapy with azathioprine 1.5-2 mg/kg/day or mycophenolate mofetil 1000 mg twice daily (or equivalent). The B cell cut off level was selected to provide a conservative selection of patients with high level of CD5+ B cells, who would be at low risk of subsequent relapse.

Patients whose CD5+ B cells remain < 43% of total CD19 B cells will receive maintenance therapy with rituximab 500 mg IV every 6 months starting when the CD19+ B cells are  $\geq 1\%$  of total lymphocytes (and CD5+ B cells are measurable) and at least 4 weeks after the last dose of cyclophosphamide (for patients who received cyclophosphamide induction therapy). [Guillevin L et al 2014]. Patients who are allergic or intolerant to rituximab or cannot access rituximab (e.g. insurance reasons) will receive maintenance therapy with azathioprine 1.5-2.0 mg/kg/day or mycophenolate mofetil 1000 mg twice daily.

[figure not shown]
**2 Study Objectives**

The primary outcome measure is time to first relapse defined as recurrence of any signs or symptoms attributable to active vasculitis after a period of complete remission with at least 2 minor or 1 major item on the BVAS score (BVAS $\geq 2$ ). Secondary outcome measures are 1) frequency and severity (as determined by BVAS score) of relapse in each group; 2) time to positive ANCA; 3) frequency and severity of infections; 4) time to IL-10 secreting B regulatory cells  $> 45\%$  or CD5+ B cells  $> 43\%$  of total B cells.

B cell subsets will be measured in the UNC Hospitals clinical lab as per our standard of care after treatment with rituximab. We will measure % of CD19+ by flow cytometry. A sample will be obtained for research analysis with each clinical sample to determine the %CD19+CD5+ B cells. For study inclusion, we will require a minimum threshold of 50 CD5+CD19+ **total detectable** events to assess this percentage. In the WATCH group, the first sample will be obtained at the time of enrollment, 6, and 12 weeks later and then at every visit subsequently until CD19+ B cell are  $\geq 1\%$ . In the maintenance therapy group, B cell subsets will be measured at the time of enrollment, and prior to each Rituximab infusion until Month 24. For subjects on maintenance therapy with azathioprine or mycophenolate mofetil, B-cell subsets will be measured at enrollment, week 22, week 46, week 70 and week 94.. Detailed B cell phenotyping and measure of IL-10 production will be performed at the same time as CD5+ analysis.

### **3.2 Primary Study Endpoints**

Primary outcome measure is time to first relapse - defined as recurrence of any signs or symptoms attributable to active vasculitis consisting of at least 2 minor or 1 major item on the BVAS score (BVAS  $\geq 2$ ) - after a period of complete remission.

### **3.3 Secondary Study Endpoints**

Secondary outcome measures are 1) frequency and severity (as determined by BVAS score) of relapse in each group; 2) time to positive ANCA; 3) frequency and severity of infections; 4) time to relapse after IL-10 producing B cells  $> 45\%$  of total B cells, compared to when CD5+ B cells are  $> 43\%$  of total B cells.

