## 5 Study Drug

### 5.1 Description

**See section 1.2**

### 5.2 Treatment Regimen

**See section 1.4**

### 5.3 Method for Assigning Subjects to Treatment Groups

All subjects whose CD5+ B cells account for less than 43% of total CD19 B cells will be assigned to maintenance therapy. Those subjects with CD5+CD19+ B cells  $\geq 43\%$  will be randomized as follows:

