### 7.2 Statistical Methods

As a proof-of-concept trial, no statistical comparisons will be done, but summary statistics and graphical displays of the data will be observed for patterns and also used to calculate sample size estimates needed for statistical comparisons in a larger trial. Summary statistical estimates of population parameters will be tabulated along with corresponding confidence intervals (CIs).

For the descriptions of each analytic Aim below groups, will be defined as follows:

Cohort 1: Subjects in remission with CD19+CD5+  $\geq 43\%$

- A) To discontinue maintenance immunosuppression (NO-Maintenance Therapy Group)
- B) To continue on maintenance immunosuppression (Maintenance Therapy Group)

Cohort 2: Subjects in remission with CD19+CD5+  $< 43\%$

- B) To continue on maintenance immunosuppression (Maintenance Therapy Group)

Aim 1. Characterize and compare A and B in terms of the outcome variables, based on data from Cohort 1.

Aim 2. Characterize and compare A and B in terms of the outcome variables, based on Cohorts 1 and 2 combined.

Aim 3. Characterize and compare Cohort 1(B) and Cohort 2(B).

Aim 4. Characterize and compare Cohort 1(A) and Cohort 2(B).

Aim 5. Obtain point- and interval-estimates needed to plan a future confirmatory randomized clinical trial.

Time to first relapse – we will summarize the time (months) to relapse and plot Kaplan-Meier curves for time to FIRST relapse by each regimen and cohort, and calculate median time to relapse and a 24-month relapse-free survival rate for each group. We will calculate a univariate hazard ratio with 95% confidence interval using Cox regression models. No statistical analyses for comparisons will be done, but trends and relapse estimates by regimen and by cohort will be used for formulating a larger study. We are most interested in time to first relapse as that denotes a clinical end point for the study since it will require reinitiating induction therapy rather than maintenance or “no maintenance”. However, we will continue to collect data on subjects with relapses for their full follow-up time to have some information on how these subjects respond to treatment and/or if they relapse again after being in this study.

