Time to first positive ANCA test (among those negative at randomization) – The percent who develop a positive ANCA test, and timing to a positive ANCA test will be summarized, with plots of time to this event using Kaplan-Meier curves generated. No statistical analyses for comparisons will be done, but trends and estimates by regimen and by cohort will be used to inform a larger study.

Frequency (number) and severity (by BVAS) of relapse – Among those who relapse, we will evaluate which organs are impacted by disease relapse (using BVAS subsections) and the severity of the relapse

(summarized by the BVAS score). This will be done by regimen and by cohort. Zero in any organ sub-section shows no disease activity in that organ. The total score range for a BVAS is 0 to 64. No statistical analyses are planned, but this will provide information for potential patterns of relapse in specific organs as well as information on the severity of relapses by group.

Occurrence of any infection – all infections will be counted and described by regimen and by cohort.

Frequency/severity/etiology of infections – recurrent infections, severity of infections, with those requiring hospitalization and/or intravenous antibiotics deemed as serious—with etiology of each infection listed. Etiologies will be listed as reported and may include a combination of location (urinary tract, upper respiratory, lung) and type of pathogen (bacterial, viral, fungal or parasitic). All infection metrics (recurrent, severity and type) be described and tallied within each regimen and cohort, but no statistical comparisons will be done. This information is necessary to understand the expected infectious adverse events that can be expected in a larger study.

Frequency and severity of any adverse advent (AEs and SAEs) – These will be catalogued as above for infections – including type of event, relation to therapy/discontinuation of therapy, and outcome of adverse event.

Time to B-cell normalization (that is, % IL-10 Secreting > 45% or % CD5+ B Cells Response > 43%) – the number who normalize will be evaluated; time to normalization will be observed in Kaplan-Meier plots by each regimen and cohort, but no statistical tests will be done to compare groups. These measures will guide the optimal times for follow-up and monitoring in a larger study.

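### Secondary endpoint 4 in section 3.3 times relapse from two different marker-crossing dates, so in Cohort 1 the comparison cannot show what either marker predicts

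*Combined protocol and SAP*

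**What the plan says.** The fourth secondary endpoint appears in three places, and they differ.

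- **Section 3.3** lists "time to relapse after IL-10 producing B cells" pass 45%, and continues "of total B cells, compared to when CD5+ B cells are" above 43%. This is a relapse time counted from a marker crossing, set against a second marker crossing. The section does not say whether the comparison is within a patient or between sets of patients. It has no rule for patients who never cross, who relapse before crossing, or who are above a threshold at enrollment.
- **Section 2** gives the fourth outcome as "time to IL-10 secreting B regulatory cells" above 45%, or CD5+ above 43%. There is no relapse clock.
- **Section 7.2** analyses "Time to B-cell normalization (that is, % IL-10 Secreting > 45% or % CD5+ B Cells Response > 43"%), by Kaplan-Meier plots of time to normalization. It plots time to first relapse by regimen and cohort, not from a marker crossing.

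Two further provisions fix when the clocks can start. Under section 5.3, patients below 43% CD5+ are assigned to maintenance, and those at or above 43% "will be randomized as follows"; section 7.2 defines Cohort 1 by the same cut. Section 3.1 says: "Detailed B cell phenotyping and measure of IL-10 production will be performed at the same time as CD5+ analysis".

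**The concern.** A time to relapse is interpretable only against its origin. Section 3.3 compares two such times with different origins, and in Cohort 1 one origin is fixed by the entry rule. Every Cohort 1 patient has met the CD5+ condition at the enrollment sample, while IL-10 is read on the same samples and can be seen to cross only then or later. The result could be read as evidence about which marker goes with staying in remission, when it partly or wholly reflects the order in which the clocks started.

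The trial is descriptive, but section 7.2 says its estimates will be used to plan a larger study. A misleading contrast between the two markers could carry into that design. The primary endpoint is not affected.

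**Working it through.** **Plan's own figure.** Section 7.1 expects about 31 patients (78%) in Cohort 1 and 9 (22%) in Cohort 2. Check: 0.78 × 40 = 31.2 and 0.22 × 40 = 8.8. The split reproduces.

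**Reading 1: within a patient.** Let C be the observed CD5+ crossing, I the observed IL-10 crossing, and R the relapse date, after both. Then

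(R − C) − (R − I) = I − C.

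R has gone. In Cohort 1, C = 0 (enrollment) and I ≥ 0, so the difference is never negative. It is zero when IL-10 is already above 45% at enrollment. The one exception is a CD5+ value of exactly 43%, which enters Cohort 1 (≥ 43%) without meeting the endpoint (> 43%).

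| Relapse (month) | CD5+ crossing | IL-10 crossing | After CD5+ | After IL-10 | Difference |
|---|---|---|---|---|---|
| 18 | 0 | 6 | 18 | 12 | 6 |
| 12 | 0 | 6 | 12 | 6 | 6 |
| 18 | 0 | 0 | 18 | 18 | 0 |
| 5 | 0 | not yet crossed | 5 | no value | none |

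Moving the relapse from month 18 to month 12 leaves the difference at 6. This step needs no assumption.

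**Reading 2: Kaplan-Meier curves from each crossing.** The documents give no IL-10 prevalence, crossing rate, relapse risk for Cohort 1 or hazard shape, so all of these are assumed.

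*IL-10 unrelated to relapse.* Inputs: CD5+ clock at week 0; IL-10 seen at the WATCH research-blood weeks in the section 6 schedule (0, 12, 22, 34, 46, 58, 70, 82, 94); Weibull relapse times. Two crossing patterns were used: 50% above the IL-10 threshold at entry and 30% of the rest crossing per sample, or 20% and 20%.

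| Hazard (assumed) | Relapse by week 106 | 12-month risk, CD5+ clock | 12-month risk, IL-10 clock (two patterns) |
|---|---|---|---|
| constant (shape 1) | 30% | 16.1% | 16.1% |
| rising (shape 2) | 40% | 11.6% | 16.6%, 20.5% |
| falling (shape 0.7) | 30% | 19.5% | 17.2%, 15.6% |

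Across these settings about 10% to 48% of relapses come before IL-10 crosses and never enter the IL-10 set. A marker with no predictive value thus appears worse, equal or better than CD5+ according to hazard shape.

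*IL-10 related to relapse.* Inputs: constant hazard, 40% risk over 104 weeks before any IL-10 effect, later crossing at a mean of 40 weeks, hazard changing at crossing. The hazard ratios tried are 1/3.7, 1 and 3.7; the 3.7 is borrowed from the CD5+ result in section 1.1 only to set a range. The 52-week risk after IL-10 crossing has the closed form 1 − 0.6^(0.5 × HR):

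- HR 1: 1 − 0.6^0.5 = 22.5%
- HR 1/3.7: 1 − 0.6^0.135 = 6.7%
- HR 3.7: 1 − 0.6^1.85 = 61.1% (simulated 60.9%)

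The simulated CD5+ clock, with 30% IL-10-high at entry, gives 22.5%, 13.0% and 46.9% respectively. With 70% IL-10-high at entry and HR 1/3.7, the pair is 9.5% (CD5+) against 6.8% (IL-10). The same IL-10 effect gives a gap of 13.0 − 6.7 = 6.3 points in one case and 9.5 − 6.8 = 2.7 in the other, because the CD5+ curve is all of Cohort 1 and the IL-10 curve is a part of it entered late.

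**Crossing dates depend on regimen.** After week 0, research blood is scheduled at weeks 12, 22, 34, 46 and so on in WATCH, but at weeks 22, 46, 70 and 94 on maintenance. An IL-10 rise at week 30 that persists is dated week 34 in WATCH and week 46 on maintenance, 12 weeks apart.

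**The case against.** Four points can fairly be made for the plan.

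1. **Pairing is not specified.** A reader might infer that endpoint 4 favours CD5+ whatever either marker predicts. The documents do not support that. Section 3.3 says only "compared to when CD5+ B cells are" above its threshold, and the plan's time-to-event displays are Kaplan-Meier curves. On those, a protective IL-10 looks better (6.7% against 13.0%). In that scenario even the crude mean time among relapsers reverses: 44.9 weeks after IL-10 against 42.4 after CD5+. The one-sided result belongs to the within-patient reading alone.
2. **No planned analysis produces the comparison.** Section 7.2 covers only time to normalization, in line with section 2. If section 3.3 is brought into line with them, the comparison disappears. This stands, and it is half of the fix. It does not help if the section 3.3 wording is the one kept.
3. **The purpose is inferred.** A reader might take the endpoint as the test that picks the marker for the larger trial. The documents never say so. Section 7.2 says the normalization measures will guide the timing of follow-up and monitoring, and assignment uses CD5+ only.
4. **The numbers are small and the sizes assumed.** With IL-10 unrelated to relapse and 20% or 40% relapse risk, only about 4 to 11 of 31 Cohort 1 patients would give a usable pair. Across the hazard ratios tried, 42% to 84% of pairs would be exact ties. Section 8.4 cites 5% major and 11% minor relapse on rituximab maintenance in an earlier trial, at most 16% together and below the 30% to 40% used in the first simulation. This limits any figure for the size of the distortion, but it does not touch the identity or its sign.

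**Conclusion.** The comparison in section 3.3 does not isolate what either marker predicts, on either reading.

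- Within a patient it is the gap between crossing dates. In Cohort 1 it can only tie or be longer after CD5+. This rests only on the entry rule and shared sampling, with the exactly-43% exception.
- Between curves started at each crossing, it loses relapses before IL-10 crosses and mixes marker effect with hazard shape and crossing time. The distortion can go either way. It is absent only if the hazard is constant and IL-10 is unrelated to relapse. The simulated sizes illustrate this under stated assumptions and are not estimates for this trial.

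The matter should be settled before analysis. Its weight is that of a secondary endpoint in a trial with no planned testing.

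**What to change.** 1. Reconcile section 3.3 with sections 2 and 7.2, and keep time to B-cell normalization as a separate descriptive endpoint.
2. If relapse by marker is wanted, define it as its own analysis with one time origin, assignment or randomization, for every patient. Describe relapse by enrollment IL-10 (continuous, and above 45% against 45% or below) and by enrollment CD5+ (continuous), separately or stratified by regimen and cohort.
3. Enter later crossings as time-dependent covariates instead of restarting the clock, and note that crossing dates are read on different sampling grids in WATCH and maintenance.

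The cost is wording. IL-10 is already measured with each CD5+ sample, including the enrollment sample. The downside is precision: with about 15 patients per randomized group, an assumed 20% to 40% risk gives 15 × 0.2 = 3 to 15 × 0.4 = 6 relapses per group before any split by marker, and Cohort 2 has about 9 patients. Intervals will be wide, and the results should be labelled descriptive only.

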### **3.4 Primary Safety Endpoints**

The primary safety endpoint will be time to relapse after randomization as defined above.

## **4 Subject Selection and Withdrawal**

### **4.1 Inclusion Criteria**

- Patients 18-85 years old.

- ANCA GN or vasculitis per Chapel Hill Consensus Criteria, with documented current or previously positive MPO- or PR3-ANCA by ELISA test. Patients with biopsy-proven, pauci-immune crescentic glomerulonephritis are eligible if they have a positive ANCA test by immunofluorescent microscopy (IIFM).
- Patients must be in complete remission for at least 1 month and after AT LEAST 3 MONTHS of induction of therapy with corticosteroids and rituximab (either 1000 mg IV x 2 or 375 mg/m^2 IV x 4) OR corticosteroids and cyclophosphamide (monthly IV or daily oral doses). They must be on no more than 5 mg daily of oral prednisone or equivalent. Complete remission is defined as a BVAS score = 0.
- Patients may be ANCA negative or positive at enrollment.
- B cells are not depleted anymore: B cell recovery reaches 1% CD19+ B cells (enough to allow determination of CD5+ B cells with confidence).

#### **4.2 Exclusion Criteria**

- Patients who have had  $\geq$  2 relapses (defined as recurrence of any signs or symptoms attributable to active vasculitis) previously as patients with multiple prior relapses may be at higher risk of future relapse and require maintenance therapy
- Patients with persistent low-grade disease activity (“grumbling” disease defined as BVAS > 0 and  $\leq$  3)
- Patients with active systemic infections or deep space infections within the 3 months prior to screening.
- Patients participating in another clinical trial mandating maintenance therapy
- Patients with drug-induced ANCA vasculitis (e.g. levamisole-adulterated cocaine)
- Active tuberculosis, human immunodeficiency virus (HIV), hepatitis C virus or hepatitis B virus infections
- For women of child-bearing potential, pregnancy, breastfeeding, unwillingness or inability to comply with effective contraception
- Inability to come to scheduled visits

#### **4.3 Subject Recruitment and Screening**

Subjects will be recruited from the UNC Kidney and Hypertension Clinic, located in the Ambulatory Care Center at UNC-Chapel Hill. Screening will be done by the designated study coordinator in concert with the principal investigator or clinical co-investigators (MDs).

#### **4.4 Early Withdrawal of Subjects**

##### **4.4.1 When and How to Withdraw Subjects, Data Collection and Follow-up for Withdrawn Subjects**

We will withdraw subjects from the study if a subject asks to be withdrawn or if a subject does not adhere to the scheduled study visits or procedures. If a patient assigned to receive maintenance therapy decides to discontinue receiving therapy, the therapy will be discontinued but we will continue following the patient and collecting data and information about the subject for the full follow up period of 24 months after randomization. If a patient in the NO maintenance therapy group shows signs of disease relapse and needs immunosuppressive therapy, s/he will be started on treatment as determined by the treating physician but we will continue to collect data and information about the subject for the full follow up period of 24 months after randomization. If a subject becomes pregnant, she will be referred to her obstetrician and will be offered to be followed with the UNC High Risk Obstetrics clinic. The managing nephrologist will decide on her care plan with respect to treating the vasculitis if it is active. If she is on treatment with rituximab or MMF, she will need to discontinue these medications. The risks/benefits of continued maintenance therapy with azathioprine will be evaluated by the treating nephrologist and obstetrician. Regardless of therapy decision, we will continue to follow her for the full follow up period.

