## **5.4 Subject Compliance Monitoring**

For patients assigned to receive maintenance therapy:

We will schedule infusion clinic visits for patients who will receive rituximab therapy and we will reschedule any missed infusion visits to ensure that they receive treatment.

We will ask patients taking mycophenolate mofetil or azathioprine questions about medication adherence at each visit and emphasize the importance of taking their medication as prescribed.

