### **6.1. Subjects randomized to NO-maintenance therapy: the WATCH group**

The subjects randomized to no-treatment will be followed up very closely:

Subjects will have study visits every 4 weeks for the first four months and then every 6 weeks for a total of 24 months of follow-up from randomization. The first visit after randomization will be Visit 1. Visit 1 will be scheduled as soon as possible after randomization.

Subjects will be called by phone by a study coordinator, nurse or physician between each clinic visit for a review of their clinical history to detect any symptoms or signs suggestive of relapse of vasculitis. Should the patient report a symptom or sign suggestive of relapse, she/he will be seen in clinic within the following week for full evaluation. The phone call will be done about 14 days after the clinic visit for the first four months and about 3 weeks after the clinic visit once the subject is followed every 6 weeks. The phone call will be done within a +/- 5 days window. Subject will be trained on the symptoms to watch for and instructed to call study team if such a symptom occurs, without waiting for study phone call or study visit.

Study visits will take place either in the UNC Kidney and Hypertension Clinic, at the Clinical and Translational Research center (CTR) or in the UNC Hospitals Infusion Clinic. Subjects will be examined by a nephrologist, either their regular nephrologist or a nephrologist who is a member of the study team. Study-specific procedures for each visit are outlined below.

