## **6.2. Subjects randomized to maintenance therapy: the treatment group**

For Subjects randomized therapy, the first rituximab infusion (or the day an alternative therapy is started) will be their Visit 1. From that day, subject will be followed in a standard of care fashion, with visits scheduled every 8 to 12 weeks, as deemed necessary by study doctor. If a participant is not scheduled for a standard of care visit within an 8-12 week window, a remote visit will be done via phone or video to collect an interim medical history.

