### 6.3.2. Treatment group

**Visit 1/ (= Week 0):** Subjects assigned to treatment groups will receive 500 mg IV rituximab (or start azathioprine or mycophenolate mofetil).

The subject will have a physical exam including BVAS and CDA assessments. We will collect information on concomitant medications and AEs. The subject will be asked to complete a quality of life questionnaire. We will collect 24 ml of blood for research purposes when the subject has blood drawn for routine labs. Women of child-bearing potential will undergo a urine pregnancy test as per indicated clinical care. We will enter the results of routine labs as well as results from B cell analysis in our study database.

**Visits 2 to 13** The subject will have a routine clinical evaluation and a BVAS assessment. We will collect information on adverse events, concomitant medications, and medication compliance. Women of child-bearing potential will undergo a urine pregnancy test as per indicated clinical care. We will enter the results of routine labs in our study database.

Subjects in this treatment groups will receive 500 mg IV rituximab at week 22, week 46, week 70 and week 94 with a +/- 1 week window (or continue azathioprine or mycophenolate mofetil). At those visits, prior to infusion, subjects will have 24 ml of blood drawn for research purposes, including analysis of B cell counts.

The visits will be between every 8 weeks to every 12 weeks, based upon the investigator assessment of how closely an individual subject needs to be followed while on maintenance therapy. The means that the subjects could have between 9 visits (if seen every 12 weeks) and 13 visits (if seen every 8 weeks) until the end of the study.

At week 106, all subjects will undergo a CDA assessment by the nephrologist.

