**Note about determination of relapse:** In cases where the assessment of relapse performed by [name] differs from that of the treating physician's assessment, the assessment used for final data analysis will be [name].

Missing Data: Missing values will not be imputed. For those who drop out of the study prior to reaching an outcome, they will contribute the time they were followed. For those who miss visits and do not have laboratory values assessed, we will use the next available to determine their time to normalization of a value. If patients report infections, we may not have details on the location or type, but will report the counts with and without patient-only reported infections (verification of infections by outside providers or hospitals will be included in the study counts and not be deemed as reported by the patient only). We anticipate minimal missing data as nearly all measures will be obtained in the setting of routine clinical practice. If patients are seen elsewhere, we will need to get outside medical records. Reasons for missing data and protocol violations will be documented in the database.

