#### Treatment Stopping Rules:

We do not have criteria for withdrawing individual subjects from the study.

If a subject in either treatment group (maintenance therapy or no maintenance therapy group) relapses, s/he will receive treatment at the discretion of the nephrologist managing his/her care. That will end the interventional phase of the subject's participation. However, we will continue to follow the subject (collect information and blood) for the full 24 months of post randomization follow up.

If a subject in the maintenance therapy group experiences a non-infectious adverse event attributable to the maintenance medication (e.g. allergic reaction) s/he is receiving (rituximab, azathioprine, MMF), this medication will be discontinued and the patient will be switched to another immunosuppressive medication per the patient's treating nephrologist.

Infectious adverse events are common in all forms of immunosuppressive therapy. Severe (Grade 3) infectious adverse events will result in temporary interruption of azathioprine or MMF therapy, or postponement of rituximab therapy, until the infection is fully treated. Grade 4 infectious adverse events will lead to the permanent discontinuation of maintenance immunosuppressive therapy. Grade 3 infectious adverse events may also lead to permanent discontinuation of maintenance immunosuppressive therapy based on the judgement of the treating physician.

If a subject in the maintenance therapy group wishes or needs to discontinue therapy, therapy will be stopped. That will end the interventional phase of the subject's participation. However, we will continue to follow the subject (collect information and blood) for the full 24 months of post randomization follow up.

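### Section 4.4.1 withdraws subjects for non-adherence, Section 8.4 says no withdrawal criteria exist, and subjects withdrawn this way have no stated follow-up and are censored for relapse

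*Combined protocol and SAP*

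**What the plan says.** **Withdrawal.** Section 4.4.1 gives two grounds for removing a subject from the study: the subject asks, or "if a subject does not adhere to the scheduled study visits or procedures". It gives no number of misses, no grace period and no definition of a procedure. Section 8.4, under Treatment Stopping Rules, states: "We do not have criteria for withdrawing individual subjects from the study".

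**Follow-up.** Sections 4.4.1 and 8.4 continue data collection for the full 24 months after a subject stops maintenance therapy or relapses, and 4.4.1 also keeps following a subject who becomes pregnant. Neither section states any follow-up for a subject withdrawn for non-adherence.

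**Analysis.** Section 7.2 (Missing Data) says: "For those who drop out of the study prior to reaching an outcome, they will contribute the time they were followed". The same paragraph uses the next available laboratory value when a visit was missed, which presumes that the subject is still in the study.

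**Contact schedule.** For WATCH, Section 6.1 says "Subjects will have study visits every 4 weeks for the first four months and then every 6 weeks for a total of 24 months" and adds "Subjects will be called by phone by a study coordinator, nurse or physician between each clinic visit". For the treatment group, Section 6.3.2 expects "between 9 visits (if seen every 12 weeks) and 13 visits (if seen every 8 weeks". If no standard-of-care visit falls in the 8-12 week window, Section 6.2 provides that "a remote visit will be done via phone or video to collect an interim medical history". For rituximab, Section 5.4 says "we will reschedule any missed infusion visits to ensure that they receive treatment". No equivalent of these two provisions is stated for WATCH.

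**The concern.** Time to first relapse is the primary endpoint (3.2) and also the primary safety endpoint (3.4). A subject removed for non-adherence before relapsing leaves the risk set at a moment chosen by the study team, and a later relapse is not captured. The Kaplan-Meier and Cox estimates in 7.2 treat that censoring as unrelated to relapse risk. People who miss visits may differ in that risk, so the assumption is doubtful.

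The rule is also discretionary. The trial is open label, so those who decide whether a subject is non-adherent know the arm. The blinded assessment in 8.4 covers relapse, not withdrawal.

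Three uses of the data are exposed:
- the 24-month relapse-free rates and hazard ratios meant to size a larger trial;
- the Section 8.4 stopping criteria and the DSMB contact after every two new relapses in the no-maintenance group, both of which depend on relapses being observed;
- the feasibility outcome in Section 1.1 on early termination and its reasons, where removals imposed by the team would be mixed with patients' own decisions.

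Scheduled contact differs by arm, so the loss could also be unequal.

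**Working it through.** **1. The texts side by side.**

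| Place | Subject who misses visits or procedures |
|---|---|
| 4.4.1 | Withdrawn from the study |
| 8.4, Treatment Stopping Rules | No criteria for withdrawal from the study |
| 7.2, Missing Data (laboratory values) | Stays in; next available value used |
| 7.2, Missing Data (dropouts) | Contributes time up to dropout |

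The first two rows cannot both be followed as written. The first and third fit poorly together. For a subject withdrawn before relapse, the fourth row is the only analysis provision that applies, and it amounts to censoring.

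**2. Contact counts.**
- WATCH visits (6.3.1 and the schedule table): weeks 0, 4, 8, 12, 16 make 5. Weeks 22 to 106 in steps of 6 make (106 − 22)/6 + 1 = 15. The total is 20. A sentence in 6.3.1 dates the change from 4-weekly to 6-weekly visits to after week 64, but the listed visit weeks match 6.1, and the count follows those.
- WATCH calls: one between consecutive visits, 20 − 1 = 19. All contacts: 20 + 19 = 39.
- Treatment visits, plan's own figure: every 12 weeks, floor(106/12) + 1 = 9, as stated. Every 8 weeks, floor(106/8) = 13 after Visit 1, or 14 counting Visit 1. The stated 13 is reproduced to within one visit.
- Ratio on clinic visits alone: 20/13 = 1.5 to 20/9 = 2.2.
- Ratio with calls counted: 39/13 = 3.0 to 39/9 = 4.3. If the four later infusions were separate attendances (13 to 17 in all), it is 39/17 = 2.3 to 39/13 = 3.0.

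**3. Can an imbalance be computed?** Two inputs are missing from the documents: the chance *p* of missing a contact, and the number of misses that counts as non-adherence. Assume *p* is equal and independent across contacts and arms. Then P(any miss) = 1 − (1 − *p*)^n, and P(m or more misses) is the upper binomial tail.

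| Assumed rule | Assumed *p* | WATCH, visits + calls (n = 39) | WATCH, visits only (n = 20) | Maintenance (n = 9) | Maintenance (n = 13) |
|---|---|---|---|---|---|
| Any miss | 2% | 54.5% | 33.2% | 16.6% | 23.1% |
| Any miss | 5% | 86.5% | 64.2% | 37.0% | 48.7% |
| 2 or more misses | 2% | 18.3% | 6.0% | 1.3% | 2.7% |
| 2 or more misses | 5% | 58.7% | 26.4% | 7.1% | 13.5% |
| At least 20% missed | 5% | 0.06% | 1.6% | 7.1% | 2.5% |

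Example: 1 − 0.98^39 = 0.545 and 1 − 0.98^9 = 0.166. In the last row the thresholds are 8 of 39, 4 of 20, 2 of 9 and 3 of 13 misses. A fixed-count rule puts more withdrawals in WATCH; the proportional rule puts more in maintenance. The sign depends on a rule that the protocol does not state.

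**4. Weight of one loss.** Section 8.4 expects about 15 per randomized group: 1/15 = 6.7%.

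**5. After the fix.** If nobody is withdrawn for non-adherence and all are followed to 24 months, censoring caused by this rule is zero in both arms. How many patients that saves cannot be fixed from the documents.

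**The case against.** A reader might infer that WATCH has three to four times the contacts and would therefore be censored far more often. The documents do not support this:
- The ratio needs all 19 staff-initiated calls to be counted. The clause names visits or procedures and does not say whether a call is either. On visits alone the ratio is 1.5 to 2.2.
- A contrast such as 55% against 17-23% treats a single miss as grounds for withdrawal. Nothing says that. The next-available-value rule, the ± one week visit window and the ± 5 day call window all suggest tolerance.
- Equal miss rates for a phone call and a clinic visit are an assumption, and a proportional threshold reverses the direction.

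There are also mitigations. People who cannot attend the planned visits are excluded (4.2), reasons for missing data are documented (7.2), all enrolled subjects are analysed (7.3), and no statistical comparisons are planned. The Section 8.4 sentence sits under treatment stopping, so it may mean only that there are no clinical grounds for removal.

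These points dispose of any claim about size or direction. They do not remove the defect. The 8.4 sentence says withdrawal from the study, and Section 5.5 shows that the protocol can separate leaving the treatment protocol from leaving data collection when it means to. Including all enrolled subjects does not recover outcomes that were never collected. A descriptive trial still hands its relapse estimates to the next design.

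**Conclusion.** The point holds as an inconsistency with a consequence for the primary endpoint. Section 4.4.1 contains a working withdrawal rule that 8.4 denies and that the handling of missed visits in 7.2 does not expect. Applied as written, it stops outcome collection on an undefined criterion judged by staff who know the arm, and the subject is censored. That could be informative censoring, and it could differ by arm: WATCH has 20 visits plus 19 calls against 9 to 13 maintenance visits, and remote substitute visits and rescheduled infusions are stated only for maintenance.

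No imbalance is demonstrated, and neither its size nor its direction can be derived. What can be said is that each lost outcome is 6.7% of an arm of 15. The conclusion rests on two readings: that a subject withdrawn by the team is handled as a dropout under 7.2, and that silence on follow-up after such a withdrawal means none is planned. The change should be made; it is inexpensive and affects data retention only.

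**What to change.** - In 4.4.1, delete the non-adherence clause, or limit it to ending study procedures while outcome follow-up continues.
- State that every assigned subject is followed for relapse and infection to 24 months by visit, phone or record review, unless consent is withdrawn.
- Record missed visits as missing data or deviations under the process that already exists (7.2 and the deviation form in 9.3).
- Bring 7.2 and 8.4 into line, so that all three sections separate ending the intervention, ending study procedures and ending data collection.
- If any adherence clause stays, define it identically for both arms and say whether a phone call counts.

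The cost is a short amendment to three sections and some extra follow-up and record requests; 7.2 already anticipates obtaining outside records. Section 8.3 makes protocol deviations reportable to the IRB, so classing every missed contact as a deviation could add reports. The amendment should say which misses are deviations and which are simply missing data.
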